**MC2-01-C6_STATISTICAL ANALYSIS PLAN_Final 3.0_07 September 2020**

Not Applicable.

13. Technical Details

Statistical analysis will be performed using SAS 9.4.

Interim and final statistical analysis report will be prepared in the Microsoft Office Word (.docx) format. The results of statistical analysis will be presented in the form of tables, figures and listings in English.

14. Summary of Changes to the Protocol

Due to small number of subjects at interim analysis geometric mean values of pharmacokinetic parameters will be directly derived from values of PK parameters calculated based on substitution of BLQ concentrations with LLOQ rather than estimated using parametric modelling. Median concentration – time plots will be omitted. Individual concentration – time plots will be presented instead.

15. References

- 1) Committee for Proprietary Medicinal Products (CPMP). International Conference on Harmonisation (ICH) Topic E9: Note for Guidance on Statistical Principles for Clinical Trials; September 1998.
- 2) DataMatrix_SOP_STAT001_Statistical Principles_ver.3.0_June 2019.
- 3) DataMatrix_SOP_STAT002_Statistical Analysis Plan Development_ver.2.0_July 2017.
- 4) DataMatrix_SOP_DM010_Dictionary Management and Data Coding_ver.2.0_August 2018.

**MC2-01-C6_STATISTICAL ANALYSIS PLAN_Final 3.0_07 September 2020****16. Listing of Tables, Listings and Figures*****16.1. Tables***

Table 14.1.1 Subject Disposition
Table 14.1.2 Violation of Eligibility Criteria
Table 14.1.4 Study Visits
Table 14.1.5.1 Protocol Deviations
Table 14.1.5.2 Major Protocol Deviations
Table 14.1.6 Demographic Characteristics
Table 14.1.7 Other Baseline Characteristics
Table 14.1.8 Baseline Characteristics by Visit
Table 14.1.9 Prior Medical Conditions/Diagnoses
Table 14.1.10 Concurrent Medical Conditions/Diagnoses
Table 14.1.11 Prior Therapy
Table 14.1.12 Concomitant Therapy
Table 14.1.13.1 Summary of Exposure and Compliance
Table 14.1.13.2 Summary of Exposure and Compliance up to Week 2
Table 14.1.13.3 Summary of Exposure and Compliance up to Week 4
Table 14.1.13.4 Summary of Exposure and Compliance from Week 4 to Week 8
Table 14.2.1.1 Individual and Summarized BDP Plasma Concentrations
Table 14.2.1.2 Individual and Summarized Betamethasone 17-propionate Plasma Concentrations
Table 14.2.1.3 Individual and Summarized CAL Plasma Concentrations
Table 14.2.1.4 Individual and Summarized MC1080 Plasma Concentrations
Table 14.2.2 Summary of Pharmacokinetic Parameters
Table 14.3.1.1 Overall Summary of TEAEs
Table 14.3.1.2.1 Incidence of Treatment-emergent Adverse Events
Table 14.3.1.2.2 Incidence of Treatment-emergent Adverse Events up to Week 4
Table 14.3.1.3.1 Incidence of Treatment-emergent Adverse Events Related to the Study Drug
Table 14.3.1.3.2 Incidence of Treatment-emergent Adverse Events Related to the Study Drug up to Week 4
Table 14.3.1.4.1 Incidence of Serious Treatment-emergent Adverse Events
Table 14.3.1.4.2 Incidence of Serious Treatment-emergent Adverse Events up to Week 4
Table 14.3.1.5.1 Incidence of Serious Treatment-emergent Adverse Events Related to the Study Drug
Table 14.3.1.5.2 Incidence of Serious Treatment-emergent Adverse Events Related to the Study Drug up to Week 4
Table 14.3.1.6.1 Incidence of Treatment-emergent Adverse Events by Maximum Severity
Table 14.3.1.6.2 Incidence of Treatment-emergent Adverse Events up to Week 4 by Maximum Severity
Table 14.3.1.7.1 Incidence of Treatment-Emergent Adverse Events by Closest Relationship
Table 14.3.1.7.2 Incidence of Treatment-Emergent Adverse Events up to Week 4 by Closest Relationship
Table 14.3.1.8.1 Incidence of Treatment-emergent Adverse Events Leading to Discontinuation of Study Drug
Table 14.3.1.8.2 Incidence of Treatment-emergent Adverse Events Leading to Discontinuation of Study Drug up to Week 4
Table 14.3.1.9.1 Incidence of Treatment-emergent Adverse Events Leading to Withdrawal

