8.7 Analysis of Pharmacokinetics

All available concentration results will be summarised using appropriate descriptive statistics for active ingredients (BDP and CAL) and for their major metabolites. Median and individual concentration versus time curves will be plotted (linear and semi-log plots).

Plasma PK parameters (AUC_{0-t} , AUC_{0-5} , C_{max} , and T_{max}) will be calculated at Week 4. The PK parameters AUC_{0-5} and C_{max} will be calculated using standard formulas inserting the LLOQ for non-quantifiable levels of the analyte; therefore, AUC_{0-5} will be an upper limit in case at least one time-point shows a non-quantifiable level of the analyte, and C_{max} will be an upper limit in case all time points show non-quantifiable levels of the analyte. For a given analyte, the PK parameters AUC_{0-t} and T_{max} will be calculated if at least one time-point shows a quantifiable level of the analyte. The PK parameters will be summarised using appropriate descriptive statistics including median, lower and upper quartiles, minimum and maximum.

A parametric model will be applied to estimate the geometric mean of C_{max} and AUC_{0-5} , respectively. The log-transformed values of the PK parameters will be assumed to be normally distributed. The mean of this normal distribution will be estimated taking the potential censoring of the values into account. The mean will then be back-transformed to the original scale as the geometric mean.

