**MC2-01-C6_STATISTICAL ANALYSIS PLAN_Final 3.0_07 September 2020**

IP before the visit. A reminder to the subject may be needed a few days before the scheduled visit.

The samples will be assayed for concentrations of the active ingredients (BDP and CAL) and for their major metabolites (betamethasone 17-propionate and MC180, respectively).

All available concentration results will be summarised by analyte and time point using appropriate descriptive statistics. Individual concentration versus time curves will be plotted (linear and semi-log plots) using actual time points.

Measured PK concentrations will be presented using standard descriptive statistics as described in section 7. Additionally, geometric mean and CV(%) will be presented.

Non-quantifiable (BLQ) levels of the analyte will be substituted by LLOQ for descriptive summaries and graphical presentation.

Plasma PK parameters at Week 4 (AUC_{0-t}, AUC₀₋₅, C_{max}, and T_{max}) will be calculated. The PK parameters AUC₀₋₅ and C_{max} will be calculated using standard formulas inserting the LLOQ for non-quantifiable levels of the analyte. For a given analyte, the PK parameters AUC_{0-t} and T_{max} will be calculated if at least one post-dose time-point shows a quantifiable level of the analyte. PK parameter values will be rounded to the precision of the raw data from which it was derived (C_{max}) or to 3 significant digits (AUC_{0-t}, AUC₀₋₅). T_{max} will be rounded to two decimal places.

Pharmacokinetic Parameters Derivations:

AUC_{0-t} (pg*h/mL): The area under the curve spanning time interval from 0 to t (up to the last time point with measurable concentration above the quantification limit) will be calculated using the linear trapezoidal rule based on actual relative time of sampling.

- 1) Actual relative time of each sample will be derived as the difference between the datetime value of the corresponding sample and the datetime value of drug application, in hours. The time of the pre-dose sample will be set to 0.
- 2) For the calculation of AUC_{0-t} BLQ values before the first reported measurable concentration (including pre-dose) will be substituted by LLOQ. The BLQ values after the last evaluable concentration will be set to missing.
- 3) Linear trapezoidal method is used. The area under the curve is defined as the sum of trapezoids across all pairs of time points from pre-dose to 5h post-dose at Visit 3 / Week 4.

Linear trapezoidal rule:

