**MC2-01-C6_STATISTICAL ANALYSIS PLAN_Final 3.0_07 September 2020**

$AUC_{t1-t2}=0.5(t_2-t_1)(C_1+C_2)$.

AUC₀₋₅ (pg*h/mL): The area under the time-concentration curve from 0 to 5 hours will be calculated in a similar way to AUC_{0-t} (pg*h/mL) while imputing the lower limit of quantification (LLoQ) for all concentrations below LLoQ.

C_{max} (pg/mL): Individual C_{max} values are directly determined from the plasma concentration time profiles of each subject as maximum of the observed concentration values after dosing. All BLQ values are substituted by LLOQ.

T_{max} (h): The time to attain C_{max}. If the same C_{max} concentration occurs at different time points, T_{max} is assigned to the first occurrence of C_{max}. If all concentrations are BLQ, T_{max} is not calculated.

The PK parameters will be summarised by analyte using standard descriptive statistics as described in section 7. Additionally, geometric mean and CV(%) will be presented for C_{max}, AUC_{0-t} and AUC₀₋₅.

11. Other Analyses

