**MC2-01-C6_STATISTICAL ANALYSIS PLAN_Final 3.0_07 September 2020**
APPENDIX 1 TFLs ShellsMC2 Therapeutics
MC2-01-C6**Table 14.2.2 Summary of Pharmacokinetic Parameters**
PK population
Page X of X

Analyte: Betamethasone dipropionate (BDP)

| | Total (N = XX) |
|------------------|-------------------|
| Cmax (pg/mL) | |
| n | XX |
| Mean | XX.XX |
| SD | XX.XX |
| gMean | XX.XX |
| gCV(%) | XX.X |
| Median | XX.XX |
| Q1, Q3 | XX.XX, XX.XX |
| Min, Max | XX.XX, XX.XX |
| AUC0-5 (pg*h/mL) | |
| n | XX |
| Mean | XX.XX |
| SD | XX.XX |
| gMean | XX.XX |
| gCV(%) | XX.X |
| Median | XX.XX |
| Q1, Q3 | XX.XX, XX.XX |
| Min, Max | XX.X, XX.X |
| AUC0-t (pg*h/mL) | |
| n | XX |
| Mean | XX.XX |
| SD | XX.XX |
| gMean | XX.XX |
| gCV(%) | XX.X |
| Median | XX.XX |
| Q1, Q3 | XX.XX, XX.XX |
| Min, Max | XX.X, XX.X |
| Tmax (h) | |
| n | XX |
| Mean | XX.XX |
| SD | XX.XX |

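### The interim geometric means of Cmax and AUC0-5 treat LLOQ-substituted values as measured, which biases them up and their geometric CV and SD down, and Table 14.2.2 does not label them as upper bounds

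*SAP*

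**What the plan says.** Protocol Section 8.7 inserts the LLOQ for non-quantifiable levels when Cmax and AUC0-5 are calculated. It calls the results upper limits and summarises them by median, quartiles, minimum and maximum. It then adds a model: "A parametric model will be applied to estimate the geometric mean of" Cmax and AUC0-5, with logs taken as normal. "The mean of this normal distribution will be estimated taking the potential censoring of the values into account".

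SAP Section 14 withdraws that model for the interim: "Due to small number of subjects at interim analysis geometric mean values of pharmacokinetic parameters will be directly derived" from parameters that rest on "substitution of BLQ concentrations with LLOQ rather than estimated using parametric modelling". SAP Section 10 sets the rule for Cmax ("All BLQ values are substituted by LLOQ"), imputes the LLOQ for all BLQ concentrations in AUC0-5, and treats single concentrations alike: "Non-quantifiable (BLQ) levels of the analyte will be substituted by LLOQ for descriptive summaries and graphical presentation". It also adds a geometric mean and CV(%) for Cmax, AUC0-t and AUC0-5. No censored-data estimate is kept.

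SAP Section 3.2.2 repeats the upper-limit wording. The shell titled "Table 14.2.2 Summary of Pharmacokinetic Parameters" prints n, mean, SD, geometric mean, geometric CV, median, quartiles and range, with no BLQ footnote and no count of censored values. The concentration shells (Tables 14.2.1.x) do carry a count of quantifiable values and an LLOQ footnote.

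**The concern.** A substituted LLOQ says only that the true value is no higher. Averaging it as if it were measured raises the geometric mean. Because all such values are identical, it also shrinks the apparent spread between subjects. An inflated mean can be defended as an upper bound, but an understated CV cannot: it makes exposure look more uniform than it is.

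Systemic exposure is the secondary objective, and Table 14.2.2 is where its parameters are summarised. Under SAP Sections 2 and 6.4 the interim report goes to FDA and the trial may then be closed permanently, so these could be the only PK results it produces.

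**Working it through.** **Inputs from the documents.** Interim n is 7 (SAP Section 6.1). Sampling at Week 4 is pre-dose and at 1, 3 and 5 h. Every BLQ value becomes the LLOQ for Cmax and AUC0-5. AUC uses actual sampling times (SAP Section 10). The LLOQ is a placeholder in the shells.

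**Assumed inputs.** The BLQ fraction and the log-scale SD (sigma) are not given. The main case uses sigma 0.8, so the true geometric CV is sqrt(exp(0.64) − 1) = 95%. The plan states no geometric mean or CV, so there is no figure to reproduce.

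**Direction for Cmax.** The reported value is max(Cmax, LLOQ). Flooring cannot lower any value, so the geometric mean cannot fall. It also cannot widen the distance between any two values, so neither SD nor geometric CV can rise.

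**Size for Cmax, large-sample limit.** Let p be the fraction of subjects whose Cmax is BLQ, z = Φ⁻¹(p) and φ the normal density.

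- m = pz + φ(z); reported/true geometric mean = exp(sigma·m)
- v = pz² + zφ(z) + 1 − p − m²; reported geometric CV = sqrt(exp(sigma²·v) − 1)

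| p | z | φ(z) | m | v | Geometric mean ratio | Geometric CV |
|---|---|---|---|---|---|---|
| 30% | −0.524 | 0.348 | 0.190 | 0.564 | exp(0.152) = 1.16 | 66% |
| 50% | 0 | 0.399 | 0.399 | 0.341 | exp(0.319) = 1.38 | 49% |
| 70% | 0.524 | 0.348 | 0.715 | 0.164 | exp(0.572) = 1.77 | 33% |

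**At n = 7.** Simulation gives the same geometric-mean ratios (about 1.16/1.4/1.8). The median geometric CV is lower still, about 61/43/25% against the true 95%.

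**Range (large-sample limit).** With a true geometric CV of 50%, the ratio runs 1.02, 1.09, 1.21, 1.40, 1.87 and the reported CV 45, 37, 28, 19, 9% at 10, 30, 50, 70, 90% BLQ. With a true geometric CV of 100%, the ratio runs 1.04, 1.17, 1.39, 1.81, 3.02 and the CV 89, 69, 52, 35, 16%.

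**AUC0-5.** Four-point profiles were simulated with each concentration floored at the LLOQ. The geometric-mean ratio was 1.09 to 3.24 over 30 to 90% BLQ samples. In one scenario a true CV of 56% was reported as 42, 27 and 10% at 30, 60 and 90% BLQ. The fall is the rule rather than a certainty: the CV rose in at most 1.4% of n = 7 samples.

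**All subjects BLQ.** Every Cmax equals the LLOQ, so SD = 0 and geometric CV = 0%. AUC0-5 varies only through actual times. Its geometric CV is about 0.6, 1.6 or 3.1% if the 5 h time varies with an SD of 2, 5 or 10 minutes. The chance of all 7 being BLQ is 0.5⁷ = 0.8%, 0.7⁷ = 8% and 0.9⁷ = 48% at 50, 70 and 90% BLQ.

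**What Table 14.2.2 reveals.** Tmax and AUC0-t are calculated only if a post-dose level is quantifiable. With complete sampling, n(Cmax) − n(Tmax) is therefore the number of upper-limit Cmax values. AUC0-5 becomes an upper limit once any one of its samples is BLQ, and no n in that table gives that count.

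**The censored fit at n = 7** (Cmax, sigma 0.8, at least 3 quantifiable subjects). At 30/50/70% BLQ the geometric mean is about 1.0/1.13/1.5 times the truth and the geometric CV about 78/73/60%. On the same data sets, log-scale root mean squared error for the censored and substituted estimates is 0.29 v 0.26, 0.26 v 0.40 and 0.44 v 0.68. The 3-subject condition is met in 1 − (1 + 7 + 21)/128 = 77% of data sets at 50% BLQ. At 70% it is met in 1 − (0.7⁷ + 7·0.3·0.7⁶ + 21·0.3²·0.7⁵) = 35%.

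**The case against.** The change is declared, has a stated reason and applies to the interim only; SAP Section 2 promises a separate SAP for any final analysis. LLOQ substitution for Cmax and AUC0-5 is the protocol's own rule, labelled there as an upper limit. Overstating exposure is the cautious direction in a maximal-use safety trial. If few values are BLQ, the effect is small. All of this stands, but none of it covers the understated CV and SD.

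A reader might infer more than the documents support:

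- **That the table hides all censoring.** It does not. The Cmax count is implicit in n for Tmax and AUC0-t. Tables 14.2.1.x show each subject's concentrations, the number quantifiable and the substitution footnote, including for the SV2 sample. What is missing is an explicit label and the AUC0-5 count where the parameters are reported.
- **That dropping the model caused the CV problem.** The protocol model covered only the geometric means of Cmax and AUC0-5. The geometric CV is a SAP addition, distorted by the substitution itself.
- **That the protocol model should return as the main estimate.** At n = 7 that is debatable. Substitution has slightly lower error at 30% BLQ, and the fit is often unavailable at 70% and remains biased up there. It has no finite estimate when all values are BLQ. No censored fit of AUC0-5 was tested, and fully quantifiable AUC0-5 values will be scarcer than quantifiable Cmax values.

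**Conclusion.** The concern holds in limited form. When values are BLQ, the interim geometric means of Cmax and AUC0-5 are biased up and their geometric CV and SD down. For Cmax the direction is algebraic; for AUC0-5 it is certain for the geometric mean and nearly always true for the CV. Under the main assumptions (n = 7, sigma 0.8, 30 to 70% BLQ) the geometric mean is overstated by roughly 16 to 80%, and a true CV of 95% is reported as about 61% down to 25%. These sizes are illustrative because the documents give no BLQ rate or sigma; with nothing BLQ there is no bias. A 0% geometric CV is exact only for Cmax and single-time concentrations, and only when all values are BLQ. The defect to correct is that Table 14.2.2 would print assay-limited statistics as though they were measured.

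**What to change.** In Table 14.2.2, for each analyte:

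- Add, for Cmax and for AUC0-5, the number of subjects with a fully quantifiable value and the number with an upper-limit value.
- Label geometric means from substituted values as upper bounds.
- When fewer than 3 subjects are quantifiable, print geometric mean, geometric CV and SD as not estimable. Show median, minimum and maximum, with '<=' on those that are limits.
- When at least 3 are quantifiable, report the protocol's left-censored lognormal estimate beside the substituted one as a sensitivity analysis.

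The cost is a few lines of SAP text, two count rows for each of the two parameters and a short censored-regression step. The downside is some blank cells and a censored estimate that is imprecise at n = 7 and still about 1.5 times the truth at 70% BLQ. The counts, labels and suppression rule are worth adopting even if the sensitivity analysis is declined.

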**MC2-01-C6_STATISTICAL ANALYSIS PLAN_Final 3.0_07 September 2020**

Table 14.3.1.9.2 Incidence of Treatment-emergent Adverse Events Leading to Withdrawal up to Week 4

Table 14.3.1.10.1 Incidence of Non-serious treatment-emergent Adverse Events Occurred at a Frequency of $\geq 5\%$

Table 14.3.1.10.2 Incidence of Non-serious treatment-emergent Adverse Events Occurred at a Frequency of $\geq 5\%$ up to Week 4

Table 14.3.1.11 Incidence of Treatment-emergent Adverse Events Related to Cosyntropin

Table 14.3.1.12 Incidence of Treatment-emergent Adverse Events Related to Study Procedures

Table 14.3.2.1 Incidence of Treatment-emergent Adverse Events Leading to Death

Table 14.3.2.2 Incidence of Treatment-emergent Adverse Events Related to the Study Drug and Leading to Death

Table 14.3.4.1.1 Summary of ACTH Challenge Test

Table 14.3.4.1.2 Incidence of HPA Axis Suppression

Table 14.3.4.2.1 Summary of Calcium Metabolism Evaluation

Table 14.3.4.3.1 Summary of Hematology Parameters

Table 14.3.4.3.2 Summary of Blood Chemistry Parameters

Table 14.3.4.3.3 Summary of Morning Urine Assessment Parameters

Table 14.3.4.4.1 Hematology Shifts from Baseline

Table 14.3.4.4.2 Blood Chemistry Shifts from Baseline

Table 14.3.4.4.3 Morning Urine Assessment Shifts from Baseline

Table 14.3.4.5.1 Incidence of Hematology Assessments Outside of Normal Range

Table 14.3.4.5.2 Incidence of Blood Chemistry Assessments Outside of Normal Range

Table 14.3.4.5.3 Incidence of Morning Urine Assessments Outside of Normal Range

Table 14.3.4.6.1 Summary of Local Skin Reactions Assessment

Table 14.3.4.6.2 Local Skin Reactions Assessment Shifts from Baseline

Table 14.3.4.6.3 Summary of LSR Sum Score

Table 14.3.4.7.1 Summary of Vital Signs

Table 14.3.4.7.2 Incidence of Vital Signs Assessments Outside of Normal Range

Table 14.3.4.7.3 Incidence of Notably Abnormal Vital Signs Assessments

Table 14.3.4.8 Summary of Physical Parameters

Table 14.3.4.9 Summary of Physical Examination

Table 14.3.4.10.1 Summary of Electrocardiogram

Table 14.3.4.10.2 Incidence of Abnormal ECG Assessments

Table 14.3.4.10.3 Incidence of Notably Abnormal ECG Assessments

Table 14.4.1.1 Summary of PGA

Table 14.4.1.2 Summary of Treatment Success

Table 14.4.1.3 PGA Shifts from Baseline

Table 14.4.2.1 Summary of Body Surface Area Involvement

Table 14.4.3.1 Summary of Psoriasis Treatment Convenience Scale

16.2. Figures

Figure 16.2.5.4 Individual BDP Plasma Concentration-time Profiles on Linear and Semi-logarithmic Scales Week 4

Figure 16.2.5.5 Individual Calcipotriol (CAL) Plasma Concentration-time Profiles on Linear and Semi-logarithmic Scales Week 4

**MC2-01-C6_STATISTICAL ANALYSIS PLAN_Final 3.0_07 September 2020**

Figure 16.2.5.6 individual MC1080 Plasma Concentration-time Profiles on Linear and Semi-logarithmic Scales Week 4

Figure 16.2.5.7 individual Betamethasone 17-propionate, Plasma Concentration-time Profiles on Linear and Semi-logarithmic Scales Week 4

16.3. Listings

Listing 16.2.1.1 Analysis Populations

Listing 16.2.1.2 Subject Visits

Listing 16.2.1.3 Study Completion

Listing 16.2.1.4 Study Treatment Completion

Listing 16.2.2.1 Violation of Inclusion/Exclusion Criteria

Listing 16.2.2.2 Protocol Deviations

Listing 16.2.4.1 Demographics and Other Baseline Characteristics

Listing 16.2.4.2 Baseline Variables

Listing 16.2.4.3 Medical History

Listing 16.2.4.4 Prior/Concomitant Therapy

Listing 16.2.4.5 Prior/Concomitant Procedures

Listing 16.2.5.1 Exposure

Listing 16.2.5.2 Study Drug Compliance

Listing 16.2.5.3 Missed Doses

Listing 16.2.5.4 Study Drug Accountability

Listing 16.2.7.1 Adverse Events

Listing 16.2.7.2 Serious Adverse Events

Listing 16.2.7.3 Listing of Adverse Events Leading Discontinuation of Study Drug

Listing 16.2.7.4 Listing of Adverse Events Leading to Withdrawal

Listing 16.2.8.1 Hematology in SI Units

Listing 16.2.8.2 Serum Biochemistry in SI Units

Listing 16.2.8.3 Morning Urine Assessment in SI Units

Listing 16.2.8.4 24-hour Urine Assessment

Listing 16.2.8.5 Serum Pregnancy Test

Listing 16.2.8.6 Urine Pregnancy Test

Listing 16.2.8.7 ACTH Challenge Test

Listing 16.2.8.8 Clinically Significant Laboratory Abnormalities

Listing 16.2.9.1 Food Diary. Calcium-rich Nutrients Consumption

Listing 16.2.9.2 Local Skin Reactions Assessment

Listing 16.2.9.3 Vital Signs

Listing 16.2.9.4 Electrocardiogram

Listing 16.2.9.5 Physical Parameters

Listing 16.2.9.6 Physical Examination

Listing 16.2.9.7 Physician Global Assessment of Psoriasis Severity

Listing 16.2.9.8 Body Surface Area Involvement

Listing 16.2.9.9 Psoriasis Treatment Convenience Scale

Listing 16.2.9.10 Pharmacokinetic Concentrations

Listing 16.2.9.11 Pharmacokinetic Parameters

**MC2-01-C6_STATISTICAL ANALYSIS PLAN_Final 3.0_07 September 2020**
APPENDIX 1 TFLs Shells**Appendix 1. TFLs Shells****Tables Shells****Subject Disposition**MC2 Therapeutics
MC2-01-C6**Table 14.1.1 Subject Disposition**
All Enrolled subjects
Page X of X

| | Total (N = XX) n (%) |
|--|----------------------------|
| Subjects who provided the informed consent / informed assent | XX |
| Screening Failures [1] | XX |
| Reasons for premature discontinuation | |
| Inconsistency with inclusion / exclusion criteria | XX |
| Withdrawal of informed consent / informed assent | XX |
| ... | XX |
| Allocated to Treatment | XX |
| Safety Population | XX |
| HPA Population | XX (XX.X) |
| PK Population | XX (XX.X) |
| Completed the Study | XX (XX.X) |
| Discontinued the Study Prematurely | XX (XX.X) |
| Reasons for premature discontinuation | |
| Inconsistency with inclusion / exclusion criteria | XX (XX.X) |
| Lost to follow-up | XX (XX.X) |
| Withdrawal of informed consent / informed assent | XX (XX.X) |
| Intake of a prohibited medication(s) | XX (XX.X) |
| Pregnancy | XX (XX.X) |
| Adverse event / Serious adverse event | XX (XX.X) |
| Investigator's discretion | XX (XX.X) |
| Sponsor's decision to terminate the study | XX (XX.X) |

